2.2 Calculation of the sample size

In the clinical study superiority hypothesis over baseline will be assessed.

The parameters of SBP, DBP and LDL-cholesterol are quantitative and changes between 12 weeks and baseline will be made, therefore, for the sample size calculation was used the following formula:

$$n = \frac{\sigma^2(Z_{1-\alpha} + Z_{1-\beta})^2}{(\mu_A - \mu_0 - \delta)^2}$$

To calculate the sample size were used the following articles:

- Dézsi, C. A. (2018). Treatment with triple combination of atorvastatin, perindopril, and amlodipine in patients with stable coronary artery disease: A subgroup analysis from the PAPA-CAD study. *Journal of International Medical Research*, 46(5), 1902-1909.

- Simon, A., & Dézsi, C. A. (2019). Treatment of hypertensive and hypercholesterolaemic patients with the triple fixed combination of atorvastatin, perindopril and amlodipine: the results of the CORAL study. *Advances in therapy*, 36(8), 2010-2020.

Systolic blood pressure

According to the literature the following assumptions were made:

- Study drug efficacy (μ_A) – mean systolic blood pressure after 3 month of therapy will be 132.2 mmHg.
- Null hypothesis drug efficacy (μ_0) - mean systolic blood pressure will be the same as at baseline – 158.5 mmHg.
- Maximum Standard deviation (σ) – 16.7 mmHg.
- Superiority margin (δ) considered as half of the difference between the drug and baseline – -13.15 mmHg (*D'Agostino Sr R. B., Massaro J. M., Sullivan L. M. Non-inferiority trials: design concepts and issues—the encounters of academic consultants in statistics //Statistics in medicine. – 2003. – T. 22. – №. 2. – C. 169-186.; Food and Drug Administration et al. Non-inferiority clinical trials to establish effectiveness: guidance for industry //US Department of Health and Human Services. – 2016.; Committee for Proprietary Medicinal Products (CPMP et al. Points to consider on switching between superiority and non-inferiority //British journal of clinical pharmacology. – 2001. – T. 52. – №. 3. – C. 223.*).
- Type I error (α) – 1%. $Z_{1-\alpha}$ – 2,326.
- Type II error (β) – 10%. $Z_{1-\beta}$ – 1.282.

The null hypothesis is formulated as:

“Change in mean systolic blood pressure after 3 month of therapy comparing to baseline will be not less than -13.15 mmHg”

$$H_0: \mu_A - \mu_0 \geq -13.15$$

The alternative hypothesis is formulated as:

“Change in mean systolic blood pressure after 3 month of therapy comparing to baseline will be less than -13.15 mmHg”

$$H_1: \mu_A - \mu_0 < -13.15$$

As a result of the calculation, it was found that in order to obtain statistically significant results, it is necessary to use data from at least 21 completed cases.

Diastolic blood pressure

According to the literature the following assumptions were made:

- Study drug efficacy (μ_A) – mean diastolic blood pressure after 3 month of therapy will be 80.1 mmHg.
- Null hypothesis drug efficacy (μ_0) - mean diastolic blood pressure will be the same as at baseline – 91.7 mmHg.
- Maximum Standard deviation (σ) – 9.9 mmHg.
- Superiority margin (δ) considered as half of the difference between the drug and baseline – -5.8 mmHg (*D'Agostino Sr R. B., Massaro J. M., Sullivan L. M. Non-inferiority trials: design concepts and issues—the encounters of academic consultants in statistics //Statistics in medicine. – 2003. – T. 22. – №. 2. – C. 169-186.; Food and Drug Administration et al. Non-inferiority clinical trials to establish effectiveness: guidance for industry //US Department of Health and Human Services. – 2016.; Committee for Proprietary Medicinal Products (CPMP et al. Points to consider on switching between superiority and non-inferiority //British journal of clinical pharmacology. – 2001. – T. 52. – №. 3. – C. 223.*).

design concepts and issues—the encounters of academic consultants in statistics //Statistics in medicine. – 2003. – T. 22. – №. 2. – C. 169-186.; Food and Drug Administration et al. Non-inferiority clinical trials to establish effectiveness: guidance for industry //US Department of Health and Human Services. – 2016.; Committee for Proprietary Medicinal Products (CPMP et al. Points to consider on switching between superiority and non-inferiority //British journal of clinical pharmacology. – 2001. – T. 52. – №. 3. – C. 223.).

- Type I error (α) – 1%. $Z_{1-\alpha} = 2,326$.
- Type II error (β) – 10%. $Z_{1-\beta} = 1.282$.

The null hypothesis is formulated as:

“Change in mean diastolic blood pressure after 3 month of therapy comparing to baseline will be not less than -5.8 mmHg”

$$H_0: \mu_A - \mu_0 \geq -5.8$$

The alternative hypothesis is formulated as:

“Change in mean diastolic blood pressure after 3 month of therapy comparing to baseline will be less than -5.8 mmHg”

$$H_1: \mu_A - \mu_0 < -5.8$$

As a result of the calculation, it was found that in order to obtain statistically significant results, it is necessary to use data from at least 38 completed cases.

LDL-cholesterol

According to the literature the following assumptions were made:

- Study drug efficacy (μ_A) – mean LDL-cholesterol level after 3 month of therapy will be 2.65 mmol/L.
- Null hypothesis drug efficacy (μ_0) - mean LDL-cholesterol level will be the same as at baseline – 3.09 mmol/L.
- Maximum Standard deviation (σ) – 1.01 mmol/L.
- Superiority margin (δ) considered as half of the difference between the drug and baseline – -0.22 mmol/L (*D'Agostino Sr R. B., Massaro J. M., Sullivan L. M. Non-inferiority trials: design concepts and issues—the encounters of academic consultants in statistics //Statistics in medicine. – 2003. – T. 22. – №. 2. – C. 169-186.; Food and Drug Administration et al. Non-inferiority clinical trials to establish effectiveness: guidance for industry //US Department of Health and Human Services. – 2016.; Committee for Proprietary Medicinal Products (CPMP et al. Points to consider on switching between superiority and non-inferiority //British journal of clinical pharmacology. – 2001. – T. 52. – №. 3. – C. 223.*).
- Type I error (α) – 1%. $Z_{1-\alpha} = 2,326$.
- Type II error (β) – 10%. $Z_{1-\beta} = 1.282$.

The null hypothesis is formulated as:

“Change in mean LDL-cholesterol level after 3 month of therapy comparing to baseline will be not less than -0.22 mmol/L”

$$H_0: \mu_A - \mu_0 \geq -0.22$$

The alternative hypothesis is formulated as:

“Change in mean LDL-cholesterol level after 3 month of therapy comparing to baseline will be less than -0.22 mmol/L”

$$H_1: \mu_A - \mu_0 < -0.22$$

As a result of the calculation, it was defined that in order to obtain statistically significant results, it is necessary to use data from at least 274 completed cases.

To obtain statistically significant results on all three primary endpoints the greatest value of calculated sample size was chosen – 274 completed cases.

Taking into account the possible drop-out rate of 30% of patients during the study, 400 patients should be included in the study.

2.3 Selection of doctors

A total of 80 general practitioners and outpatient cardiologists will participate in this non-interventional study

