2.7 Documentation of the non-interventional clinical study

2.7.1. Documentation folder

Each doctor will be provided with a documentation folder containing a complete set of documents for 5-6 patients + 2 extra sets in case of lost or damage of study documents including:

- One protocol of the observation plan;
- Documents for 5-6 patients (12 *Patient Informed Consent Forms*, with 5-6 *Adverse event/adverse drug reaction/special situation reporting forms*).
- 2 extra sets in case of lost or damage of study documents (*Patient Informed Consent Form*,; *Adverse event/adverse drug reaction/special situation reporting forms*)

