4.2 Statistical analysis

Due to the non-interventional nature of this study, statistical analysis will be carried out in descriptive and exploratory forms. All parameters will be analysed using descriptive statistics. For each parameter, the following will be specified: number of patients, mean value, standard error, minimum and maximum values, or proportion of each category. All composite endpoints will be listed and presented in visual form as graphs and in tables of parameters and their frequencies. For categorical variables, absolute values and rates in per cents be calculated. The calculations of relative rates will include only patients in whom values of the corresponding variables will be available.

Accepted level of significance

In all tests, a significance level of 0.05 will be used, and 2-sided statistical tests will be carried out.

Search statistical analysis will be performed in the following subgroups of patients:

- patients with stable CAD
- patients with diabetes mellitus type 1 or type 2
- patients with chronic kidney disease

All reports of adverse drug reactions (ARDs), adverse events (AEs), serious ADR/AE, and special situations will be encoded using MedDRA by the subcontractor, and the results will be listed and classified according to the System-Organ-Classes (SOCs). Descriptive statistics will be used.

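### Patients are grouped within 80 doctors, but neither the sample size nor the analysis allows for it, so unadjusted precision would be optimistic if patients of one doctor are alike

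*Combined protocol and SAP*

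**What the plan says.** The grouping is set out in three places. Section 2.3: "A total of 80 general practitioners and outpatient cardiologists will participate in this non-interventional study". Section 2.7.1 gives each doctor a "complete set of documents for 5-6 patients + 2 extra sets" against loss or damage. Section 2.2 concludes: "Taking into account the possible drop-out rate of 30% of patients during the study, 400 patients should be included in the study".

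The doctor has a hand in treatment and measurement. The treating investigator decides on the combination pill (2.5.1), may add or change any other drug (2.5.2), measures blood pressure and records dose corrections at the visits (2.7.2 and 2.7.4), and leaves out patients expected to adhere poorly (2.4.2, criterion 4).

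Section 2.2 uses a one-sample formula for independent observations at one-sided 1% and 90% power. LDL-C drives the result: "the greatest value of calculated sample size was chosen – 274 completed cases". The formula has no design effect, and no ICC is mentioned.

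Section 4.2 asks for "number of patients, mean value, standard error, minimum and maximum values, or proportion of each category" and sets a two-sided 5% level for all tests. It names no doctor or site effect, mixed model or cluster-robust variance, and it does not say how standard errors are to be computed. It calls the analysis descriptive and exploratory. Confidence intervals are mentioned only in the SF-36 appendix.

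**The concern.** Patients of one doctor share prescribing habits, measuring technique and judgements about who is suitable. If their changes in blood pressure or LDL-C are therefore more alike than those of patients of different doctors, 280 completers carry less information than 280 independent patients. The usual standard error is then too small, intervals are too narrow, and a 5% test rejects more often than 5% of the time under the null.

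This matters most for the three primary changes, for which section 2.2 states formal null hypotheses, and for the association and predictor analyses listed in section 1.3. LDL-C has little room within section 2.2's own terms: 280 completers expected against 274 required.

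**Working it through.** **Inputs.** From 2.2: LDL-C "mean LDL-cholesterol level will be the same as at baseline – 3.09 mmol/L" under the null; "mean LDL-cholesterol level after 3 month of therapy will be 2.65 mmol/L"; margin -0.22, SD 1.01, z-values 2.326 and 1.282, 400 enrolled, 30% drop-out. From 2.3: 80 doctors. Assumed, because the documents give none: ICC 0.01, 0.02, 0.05 and 0.10.

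**Step 1. The plan's own figure.** The expected change is 2.65 - 3.09 = -0.44, which lies 0.22 beyond the margin.

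n = 1.01² × (2.326 + 1.282)² / 0.22² = 1.0201 × 13.018 / 0.0484 = 274.4, against 274 stated.

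The same formula gives 21.0 for SBP (stated 21) and 37.9 for DBP (stated 38). Drop-out: 274/0.7 = 391.4, so 392, taken up to 400; 400 × 0.7 = 280 completers. All figures reproduce with no clustering term.

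**Step 2. Design effect.** Mean cluster size m = 280/80 = 3.5, and DE = 1 + (m - 1) × ICC = 1 + 2.5 × ICC.

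**Step 3. Consequences.**

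- Shortfall of the unadjusted standard error = 1 - 1/√DE
- Real error of a nominal two-sided 5% test = 2 × [1 - Φ(1.96/√DE)]
- LDL-C power against the margin = Φ(0.22 × √(280/DE)/1.01 - z), with z = 2.326 (section 2.2) or 1.96 (section 4.2)

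| ICC (assumed) | DE | SE too small by | Real error of 5% test | Power, one-sided 1% | Power, two-sided 5% |
|---|---|---|---|---|---|
| 0 | 1 | 0% | 5.0% | 90.6% | 95.4% |
| 0.01 | 1.025 | 1.2% | 5.3% | 89.9% | 94.9% |
| 0.02 | 1.05 | 2.4% | 5.6% | 89.1% | 94.5% |
| 0.05 | 1.125 | 5.7% | 6.5% | 86.6% | 93.0% |
| 0.10 | 1.25 | 10.6% | 8.0% | 82.5% | 90.3% |

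At ICC 0.10 the half-width of the 95% interval for the LDL-C change goes from 1.96 × 1.01/√280 = 0.118 to 0.118 × √1.25 = 0.132 mmol/L.

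**Step 4. Blood pressure.** With 280 completers against 21 and 38 needed, SBP and DBP power stays above 99.9% over the whole range.

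**Step 5. Unequal recruitment.** If the number of completers per doctor varies with a coefficient of variation of 0.5 (assumed), DE = 1 + (1.25 × 3.5 - 1) × ICC. That is 1.17 at ICC 0.05 and 1.34 at ICC 0.10. LDL-C power at one-sided 1% becomes 85.2% and 79.5%. At two-sided 5% and ICC 0.10 it is Φ(0.22 × √(280/1.3375)/1.01 - 1.96) = Φ(1.19), about 88%.

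**The case against.** The strongest reply is that nothing in the documents shows the ICC to be above zero, and that the primary variables are within-patient changes. A doctor's constant measuring habit or a fixed laboratory offset cancels from a change when the same source supplies both values. That stands in part: it is a reason to expect a smaller ICC. It does not remove the issue, because baseline values come from earlier records (2.1) and because treatment choices act on the change itself.

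A second reply is that power is safe. At section 4.2's two-sided 5%, LDL-C power stays at or above 90% up to ICC 0.10 if doctors recruit equally. The SD of 1.01 is also the baseline SD of the 3-month study described in 1.1, whose follow-up SD is 0.82. At an assumed correlation of 0.5, the SD of change is √(1.01² + 0.82² - 2 × 0.5 × 1.01 × 0.82) = 0.93, which absorbs a design effect of about (1.01/0.93)² = 1.18. These offsets are fair, but they concern power. They do not correct a standard error or an error rate.

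A third reply is that the study is descriptive and that the headline would survive. A change of -0.44 is 7.3 standard errors from zero at n = 280, and still 6.5 at a design effect of 1.25. That is true of the comparison with zero. Section 2.2 tests against -0.22, however, and a reported standard error is a statement about precision in a descriptive study too.

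Stronger readings that a reader might infer are not supported:

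- That the intervals are too narrow as a matter of fact. This depends on an ICC that the documents do not give.
- That section 4.2 prescribes standard errors assuming independence. It leaves the method open.
- That every target proportion is affected. Section 4.2 plans only counts and percentages for categorical variables. The blood pressure targets split by age, risk and dose form 2 × 3 × 3 = 18 cells, about 280/18 = 16 completers each if evenly spread. Few doctors would have more than one patient in a cell, so the design effect is near 1 unless doctors strongly favour one dose.
- That a shared local laboratory drives the LDL-C correlation. The documents do not say which laboratories are used.
- That enrolment must rise. Holding 90% power at one-sided 1% with 80 doctors and ICC 0.10 would take about 376 completers (537 enrolled), but that rests on an assumed ICC and a probably cautious SD.

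**Conclusion.** The point holds in a conditional form. The grouping by doctor is certain, and neither section 2.2 nor section 4.2 accounts for it. If the within-doctor correlation is positive, unadjusted precision for the primary changes is overstated: negligibly at ICC 0.01 to 0.02, and moderately at 0.05 to 0.10, where the standard error is about 6% to 11% too small and a 5% test has a real error of 6.5% to 8.0%. The loss of power concerns LDL-C only, and only under section 2.2's one-sided 1% does it fall clearly below the planned 90% with equal recruitment. These sizes rest on the assumed ICC range, 280 completers, 80 recruiting doctors and roughly equal numbers per doctor; uneven recruitment makes them larger. The change is worth making because it costs almost nothing, not because a main conclusion is shown to be at risk.

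**What to change.** In section 4.2, state that standard errors, intervals and p-values will be computed with the doctor as cluster, by cluster-robust errors or a doctor random intercept. This should cover the changes in SBP, DBP and LDL-C, any intervals reported for the overall target proportions (not the small age-by-risk-by-dose cells), and the association and predictor analyses.

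In section 2.2, add the LDL-C power over an assumed ICC range of 0.01 to 0.10, labelled as an assumption. Leave enrolment at 400. When doing so, reconcile the one-sided 1% of section 2.2 with the two-sided 5% of section 4.2, since the power figure depends on which applies.

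The cost is about one sentence in each section and slightly wider intervals. No patients, visits or measurements are added. Documentation is issued per doctor (2.7.1) and each investigator keeps the patient identification list (5.1), so the doctor should be identifiable for every record; the data set needs to carry that identifier. Eighty clusters are enough for cluster-robust methods to be workable.

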2.4 Selection of patients

2.4.1 Inclusion criteria

1. Obtained signed informed consent from the patient
2. Patients of 18 years and older and younger than 80 years.
3. Start of the treatment with SPC of amlodipine/atorvastatin/perindopril within 1 month from the Index date in accordance with the indication in Russian SmPC.
4. Presence of the parameters of interest* in the medical records dated with the nearest to the start of SPC amlodipine/atorvastatin/perindopril treatment date.

* Parameters of interest include measured at rest office BP and LDL-C.

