1.2 Objectives

Primary objective is to describe antihypertensive and hypolipidaemic effectiveness of a triple single-pill combination of amlodipine, atorvastatin and perindopril at 12 weeks in patients with arterial hypertension (HTN) and dyslipidemia in the daily clinical practice.

Secondary objectives

- To determine the proportion of patients who reached systolic (SBP) and diastolic blood pressure (DBP) target goals at weeks 4 and 12 of the observation period respectively.
- To determine the proportion of patients who reached LDL-C target goals at week 12 of the observation period.
- To evaluate the quality of life of patients at visit 1 (V1) and visit 2 (V2) as compared to visit 0 (V0) respectively.
- To evaluate the adherence to treatment with the fixed dose combination (FDC) of amlodipine/atorvastatin/perindopril in patients included into the study at V1 and V2 as compared to V0.
- To evaluate predictors of reaching BP and LDL-C target goals in the study population.

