1.3 Study variables

Primary variables:

- Mean change from baseline (BL) in SBP and DBP assessed at week 12 of the observational period.
- Mean change from BL in LDL-C assessed at week 12 of the observational period.

Secondary variables:

- Mean change from BL in SBP and DBP assessed at week 4 of the observation period.
- Proportion of the patients aged 18-64 years who reached SBP <140 mm Hg and DBP <90 mm Hg at week 4 of the observation period.
- Proportion of patients aged 18-64 years who reached target SBP <130 and \geq 120-mm Hg and DBP between 70 and79 mm Hg at week 12 of the observation period.
- Proportion of patients older than 65 years who reached SBP < 140 mm Hg and DBP < 90 mm Hg at week 4 of the observation period.
- Proportion of patients older than 65 years who reached SBP \leq 139 and \geq 130 mm Hg and DBP between 70 and79 mm Hg at week 12 of the observation period.
- Proportion of patients at very high CV risk who reached LDL-C decrease \geq 50% from BL and reached target < 1,4 mmol/l (55 mg/dl) or at week 12 of the observation period.
- Proportion of patients at high CV risk who reached LDL-C decrease \geq 50% from BL and reached target LDL-C < 1,8 mmol/l (70 mg/dl) at week 12 of the observation period.
- Proportion of patients at moderate CV risk who reached target LDL-C < 2,6 mmol/l (100 mg/dl) at week 12 of the observation period.
- Proportion of patients at different CV risk who reached both BP and LDC-C targets
- Proportion of patients aged 18-64 years at very high CV risk who reached SBP <130 and \geq 120 mm Hg and DBP between 70 and79 mm Hg at week 12 of the observation period in the subgroups of the patients receiving SPC of amlodipine/atorvastatin/perindopril in the following dosages 5;20;5 mg and 5;20;10 mg and 5;10;5 mg respectively;
- Proportion of patients older than 65 years at very high CV risk who reached SBP \leq 139 and \geq 130 mm Hg and DBP between 70 and79 mm Hg at week 12 of the observation period in the subgroups of patients receiving SPC of amlodipine/atorvastatin/perindopril in the following dosages 5;20;5 mg and 5;20;10 mg and 5;10;5 mg respectively
- Proportion of patients at very high CV risk who reached LDL_C decrease \geq 50% from BL and reached target <1,4 mmol/l (55 mg/dl) or at week 12 of the observation period in the subgroups of the patients receiving SPC of amlodipine/atorvastatin/perindopril in the following dosages 5;20;5 mg and 5;20;10 mg and 5;10;5 mg respectively;

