2.1 Study design with the rationale for its' choice

This is a multi-centre, observational, ambispective study, which will retrospectively and prospectively collect clinical and socio-demographic data from medical records of patients with HTN and dyslipidemia initiated with SPC of amlodipine/atorvastatin/perindopril in real clinical settings.

For parameters of the primary end-point such as BP and LDL-C **a Baseline data** is defined as values of these parameters present in medical records at the nearest date preceding the start of SPC amlodipine/atorvastatin/perindopril. Therefore BP and LDL-C **Baseline data** will be collected retrospectively from medical records of patients with HTN and dyslipidemia. To be included in the study for further prospective observation a patient should have been administered with SPC of amlodipine/atorvastatin/perindopril within one month before the Index Date. The Index date is a date when a decision to include a patient in the study for further 12 week prospective observation made by a treating physician after evaluation of recorded data to confirm patient's eligibility for the study. Once an investigator makes sure that a patient meets all inclusion/non-inclusion criteria the investigator will discuss with the patient during his/her next visit and obtain the signed patient's informed consent to participate in the study (V0).

SPC of amlodipine/atorvastatin/perindopril will be administered to the patients in accordance to the instruction for medical use approved in the Russian Federation. Decision on this medicinal product administration will not be dependent on the decision to include a patient into the observational study and according to the study protocol, such decision should precede treating investigator's intention to include a patient in the study.

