2.4.2 Non-inclusion criteria

1. Subjects who are unwilling or unable to provide a signed informed consent form;
2. Any contraindication to the treatment with the SPC of amlodipine/atorvastatin/perindopril according to its' approved instruction for medical use in the Russian Federation;
3. Concomitant use of any other ACE inhibitors, CCBs, ARBs and statins.
4. Supposed low treatment adherence to the assigned SPC and the risk for poor collaboration between the patient and the investigator during the study;
5. Any severe, decompensated or unstable somatic diseases or states that according to investigator discretion are life-threatening or worsen the prognosis for the patient: myocardial infarction in the past 3 months, unstable angina, current decompensation of diabetes mellitus, autoimmune or oncological diseases, severe cardiac arrhythmia,

gastrointestinal disorders affecting absorption, severe hepatic diseases, pancreatic diseases, severe allergic reactions, connective tissue diseases etc;

6. Secondary arterial hypertension;
7. Alcohol or any drug abuse;
8. Surgical intervention on heart or coronary vessels (i.e., heart valve(s) replacement, stent implantation or CABG), or any non-cardiological serious surgical intervention that are planned within next 3 months and may require withdrawal or changes in current therapy;
9. Glomerular filtration rate less than 60 ml/min/1,72m²;
10. Participating in any other clinical trial currently or during 30 days period before informed consent was signed.

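### The secondary target proportions have no baseline counterpart, so patients already at target before the SPC count as having reached it, chiefly for moderate-risk LDL-C

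*Combined protocol and SAP*

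**What the plan says.** **Entry.** Criterion 4 in Section 2.4.1 requires "Presence of the parameters of interest* in the medical records dated with the nearest to the start of SPC", and its footnote reads "Parameters of interest include measured at rest office BP and LDL-C". Neither Section 2.4.1 nor Section 2.4.2 sets a minimum value. Criterion 3 requires that the SPC was started "in accordance with the indication in Russian SmPC", but the text of that indication is not in the documents. Appendix 8 lets any one of several lipid values qualify as dyslipidemia, so LDL-C itself need not be raised. Non-inclusion criterion 3 bars "Concomitant use of any other ACE inhibitors, CCBs, ARBs and statins". It does not bar earlier use of those classes, so a patient switched from effective treatment can enter.

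**Baseline.** Section 2.1 defines it for BP and LDL-C as "values of these parameters present in medical records at the nearest date preceding the start of SPC amlodipine/atorvastatin/perindopril". It is therefore held for every patient.

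**Targets.** One secondary objective in Section 1.2 is "To determine the proportion of patients who reached LDL-C target goals at week 12 of the observation period". Among the variables in Section 1.3 are "Proportion of patients at moderate CV risk who reached target LDL-C" (<2.6 mmol/l at week 12) and "Proportion of the patients aged 18-64 years who reached SBP <140 mm Hg and DBP <90 mm Hg at week 4", with the same week-4 limits for the older age group. The week-12 BP targets are bands: SBP from 120 to below 130, or 130 to 139, each with DBP 70 to 79. For high and very high risk, the LDL-C variables require a decrease of at least 50% from baseline and also a value below 1.8 or 1.4 mmol/l. The very-high-risk wording contains a stray _or_, and Appendix 6 gives the threshold or the 50% decrease as alternatives.

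**Use of baseline.** Baseline values enter the mean changes, which include the primary variables, and the association and predictor variables. No proportion at target at baseline is listed.

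**The concern.** This is a single-arm study, so baseline is the only comparator. Section 1.1 hopes that the combination will raise the percentage of patients at both BP and LDL-C targets. An increase cannot be shown without the starting percentage. Section 1.1 also reports that 20% of Russian patients with hypertension reach target BP and 17.4% reach target LDL-C, so a starting percentage of zero cannot be assumed.

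Where success depends only on the follow-up value, reaching target and staying at target cannot be told apart. The predictor analyses share the problem: if patients already below 2.6 mmol/l are included, a low baseline LDL-C predicts success partly by construction.

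**Working it through.** **1. The plan's own figure.** The plan gives no at-target share at baseline. Its planning inputs do reproduce its sample size. For LDL-C (Section 2.2: 3.09 to 2.65 mmol/L, maximum SD 1.01, margin −0.22):

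n = 1.01² × (2.326 + 1.282)² / (−0.44 + 0.22)² = 274.4, against 274 stated.

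SBP (21) and DBP (38) reproduce in the same way. No target proportion enters these calculations.

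**2. LDL-C <2.6 mmol/l.** Assume a normal distribution and that the overall mean and SD hold in the moderate-risk stratum. The share below target is Φ((2.6 − mean)/SD).

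| Inputs | Baseline | Follow-up | Ratio |
|---|---|---|---|
| Section 2.2: 3.09 to 2.65, SD 1.01 at both | Φ(−0.49) = 31% | Φ(−0.05) = 48% | 0.314/0.480 = 0.65 |
| Section 1.1 (cited 3-month study): 3.41 ± 1.01 to 2.80 ± 0.82 | Φ(−0.80) = 21% | Φ(−0.24) = 40% | 0.211/0.404 = 0.52 |

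The ratio is a ceiling on the share of successes already at target at baseline, because it supposes that all such patients stay there. A lognormal shape gives baseline shares of 35% and 21%.

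**3. BP <140/<90 (week 4).** Section 1.1 gives 158.5 ± 16.7 / 91.7 ± 9.4 mmHg before treatment.
- SBP alone: Φ((140 − 158.5)/16.7) = 13.4%.
- DBP alone: Φ((90 − 91.7)/9.4) = 42.8%.
- Both, uncorrelated: 0.134 × 0.428 = 5.7%. Both, at an assumed correlation of 0.7: 11.9% (bivariate normal).

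The documents give no week-4 mean. The 3-month values (132.2 ± 8.3 / 80.1 ± 6.8) imply 77% to 80% at target. Using these as a stand-in, the ceiling is 0.057/0.766 = 7% to 0.119/0.804 = 15% of successes.

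**4. Week-12 BP bands.** With the same inputs, BP rounded to whole mmHg and correlation 0 to 0.7, the baseline share is 0.3% to 1.4% for 120–129/70–79 and 0.8% to 2.6% for 130–139/70–79. At 3 months the implied shares are 13% to 20% and 16% to 18%. At most 3 percentage points could be carried over. Even that supposes that patients stay inside a 10 mmHg band while mean SBP falls by 158.5 − 132.2 = 26.3 mmHg.

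**5. High- and very-high-risk LDL-C.** Read with _and_, a high-risk patient who starts at 1.7 mmol/l succeeds only at 0.5 × 1.7 = 0.85 mmol/l or lower, so being at the threshold beforehand is not enough. Read with _or_, such a patient succeeds by staying put. On the inputs of step 2, baseline shares would then be 6% to 10% below 1.8 and 2% to 5% below 1.4 mmol/l.

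**The case against.** The strongest reply is that these are secondary, descriptive proportions in a non-interventional study. The primary variables are mean changes from baseline, which a patient already at target does not distort in this way. Baseline values are held for everyone, and their association with reaching target is already a listed analysis. All of this stands. It limits the importance of the point, but a mean change or an association does not give the starting percentage.

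Three stronger readings are tempting, and the documents do not support them.
- _The missing entry threshold is itself a defect._ Enrolment follows routine prescribing within the label, and a label limit that cannot be seen may apply. The gap lies in what is reported.
- _Every target variable counts patients already at target._ As written, the high- and very-high-risk LDL-C variables do not do so automatically, and the week-12 BP bands hold under 3% of patients at baseline on the planning figures. Because they are bands, a value below them is not a success, so a low baseline does not simply predict success there.
- _The predictor models should be confined to patients above target._ That changes the question and selects on high recorded values, which invites regression to the mean. It suits a sensitivity analysis, not a replacement.

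**Conclusion.** The point holds in limited form. For moderate-risk LDL-C, at most about half to two thirds of the patients reported as reaching <2.6 mmol/l could have been there before the SPC. For week-4 BP the baseline share is about 6% to 12%. The variables that combine BP and LDL-C targets, or split the moderate-risk LDL-C target by dose, inherit the problem. High- and very-high-risk LDL-C is affected only under the _or_ reading.

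These figures are illustrations. They rest on normality, on an assumed SBP–DBP correlation, and on overall means applied to one risk stratum, although Section 2.2 draws partly on a study in stable coronary disease, which may differ from moderate-risk patients. The size of the moderate-risk stratum and the true baseline shares are unknown. A reader might infer that the effectiveness conclusion as a whole is unsafe. The documents do not support that on this ground, since the primary mean changes and the sample size do not depend on these proportions.

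**What to change.** Before analysis, add to Sections 1.3 and 4.2:
- For each absolute threshold or band, the proportion at target at baseline beside the follow-up proportion, in patients with both values, with the paired change and its 95% CI. Baseline here should be the pre-SPC record defined in Section 2.1, not the V0 reading, which is taken after the SPC was started.
- The proportion reaching target among patients not at target at baseline, with a note that regression to the mean affects this subset.
- The planned predictor models unchanged, plus a sensitivity fit in patients not at target at baseline.

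Separately, reconcile the _and_/_or_ wording of the LDL-C targets between Section 1.3 and Appendix 6. For these groups the baseline comparison can use only the absolute threshold, because a decrease from baseline has no baseline value.

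The cost is a little more analysis of data already collected, with no new visits, tests or patients. The sensitivity fit will be less precise because it drops patients. The target-attainment results will look less favourable.
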